Prospective studies have shown that 17 hydroxyprogesterone caproate (17OHP-C) significantly decreases rates of preterm birth (PTB). Low levels of plasma 17OHP-C are associated with increased risks of spontaneous PTB. Emergency data suggest 17OHP-C may be less efficacious in obese women. Since obesity is associated with lower levels of plasma 17OHP-C, we hypothesize that higher doses of 17OHP-C may help to prevent spontaneous PTB among obese women. We propose a prospective study including a randomization of obese women with the following specific aims:

Primary Aim: Determine if a higher weekly dose of 17 OHP-C in obese women results in a higher maternal plasma levels compared with the standard 250mg weekly dose.

Hypothesis: A 500mg weekly dose of 17OHP-C will produce higher maternal plasma levels in obese compared to the standard 250 mg dose.

We will randomly assign obese women with a prior history of spontaneous PTB to 250 mg or 500 mg weekly doses of 170HPC, and compare mean plasma levels of 170HP-C in obese women receiving 500 mg to obese women receiving 250 mg as well as non-obese women receiving 250 mg.

Secondary Aim: Determine the relationship between maternal 17-OHPC levels and gestational age at delivery.

Hypothesis: Higher doses of 17OHP-C will be associated with high gestational age of delivery in obese women.

We will compare the mean gestational age at delivery of obese women receiving 250 mg to obese women receiving 500 mg as well as non-obese women receiving 250 mg.

B. Background

PTB continues to be the leading cause of neonatal morbidity and mortality in the United States, affecting 9.57% of all births in 2014. ^{1, 2} The impact of PTB is far reaching. Consequences of PTB include numerous detrimental short and long-term outcomes for the premature infant, ³⁻⁶ impaired maternal and paternal psychological health, ^{7, 8} and steep personal and societal costs. ⁹⁻¹³ Several strategies have been

introduced to decrease rates of PTB. In addition to nationwide campaigns aimed at reducing iatrogenic preterm deliveries, ¹⁴ national organizations have issued protocols outlining appropriate candidates for 17 alpha hydroxyprogesterone caproate (17OHP-C), vaginal progesterone, and cerclage – all of which have been shown to decrease rates of PTB among specific populations.^{1, 15, 16}

Among women with a history of a spontaneous PTB, 17OHP-C has been shown in a randomized trial to decrease the risk of a subsequent PTB by 33%. In this study including 463 women, the number needed to treat to prevent one PTB prior to 37 weeks was only 5 to 6 women. ¹⁷ In addition to effectively reducing the recurrence of PTB, mathematical modelling has demonstrated that administration of 17OHP-C to women with a prior spontaneous PTB could lead to future cost savings.^{18, 19} The individual and societal benefits of 17OHP-C are clear. However, questions remain about optimal dosing of 17OHP-C among obese women. As the prevalence of obesity in the United States exceeds 35%, optimizing interventions to prevent PTB in this population has significant public health implications.

Obesity causes several physiological changes than can impact medication pharmacokinetics. Some changes include increased blood volume and increased cardiac output which can lead to varied distribution patterns and potentially a change in medication absorption.^{20, 21} Caritis et al. demonstrated that body mass index (BMI) was inversely correlated with trough plasma 17OHP-C concentrations and the area under the plasma concentration versus time curve. These data suggest that higher dosing may be needed for obese patients.²² A similar conclusion was reached in a secondary analysis of a Maternal-Fetal Medicine Unit Trial. Among 443 women, treatment with 17OHP-C in obese women or with a weight of > 165 pounds did not appear to decrease the rate of PTB.²³ Moreover, additional studies have shown that low plasma 17OHP-C levels ²⁴ and a maternal pre-pregnancy BMI of $\ge 25 \text{ kg/m}^2$ are associated with higher rates of spontaneous PTB.²⁵

Conversely, other retrospective studies report that spontaneous PTB rates among normal weight as compared to obese women are similar suggesting that current 17OHP-C dosing guidelines are sufficient.²⁶ Literature supporting optimal dosing of 17OHP-C for obese patients is lacking and current clinical studies report conflicting information.

C. Study Design

Prospective three arm study of women with a prior spontaneous PTB. Non-obese women will receive the standard 250 mg weekly dose of 17 OHP-C while obese women will be randomly assigned to the standard (250 mg) or higher dose (500 mg). The resulting three groups will consist of:

- 1. Normal weight women on 250mg 170HPC
- 2. Obese women on 250mg 170HPC
- 3. Obese women on 500mg of 170HPC
- a) Subjects

Pregnant patients receiving prenatal care at these University of South Florida (USF) and Washington University affiliated locations will be eligible:

- Genesis Healthpark
- South Tampa Center
- Washington University (Barnes Jewish Hospital) in St. Louis

b) Inclusion / Exclusion Criteria

Inclusion Criteria

- Pregnant women, with a singleton gestation
- Ages 18 55
- Able to read and write in English and / or Spanish
- History of spontaneous PTB
- Obesity (≥ 30 kg / m²) vs non-obese groups (18 29.9 kg / m²) defined by first documented body mass index at an office visit
- Gestational age between 12 weeks, 0 days and 24 weeks, 6 days of gestation
- An ultrasound before 24 + 6 weeks gestation to confirm dating and to rule out major fetal anomalies
- Willing to have weekly injections at the physician's office
- The newborn will be enrolled on the mothers consent for chart review only

Exclusion Criteria

- Multifetal gestation
- Known fetal anomaly
- Current progesterone treatment
- Known or suspected breast cancer, other hormone-sensitive cancer, or history of these conditions
- Current or history of thrombosis or thromboembolic disorder
- Current anticoagulation
- Undiagnosed abnormal vaginal bleeding unrelated to pregnancy

- Cholestatic jaundice of pregnancy
- Liver tumors, benign or malignant, or active liver disease
- uncontrolled hypertension (controlled hypertension is eligible)A seizure disorder
- Current or planned cervical cerclage
- Plan to deliver elsewhere

c) Research Design and Methods

Initial Enrollment: Pregnant patients receiving prenatal care at one of the USF affiliated sites or Washington University in St. Louis sites who report a history of a PTB will be approached by the research nurse. The research nurse will explain the study, review inclusion/exclusion criteria with the patient, and invite interested potential study candidates to sign a medical records release so that records from the previous PTB can be reviewed. If the medical records confirm the birth of a previous PTB was of a live born singleton gestation between the gestational ages of 20 weeks and 36 weeks and 6 days then the patient will be invited to participate in the study. At that time the informed consent form will be thoroughly reviewed with the patient, and if the patient desires to enroll, she will provide informed consent to enroll in the study. Consecutive women with normal BMI or obese women meeting the inclusion criteria will be approached to avoid selection bias.

Randomization: will occur at the time of enrollment. The randomization will be computer generated. Randomization envelopes indicating the randomization arm will be prepared ahead of time and the next consecutive envelope will be used at time of enrollment.

Preparation of study drug: Participants in the 250 mg of 17OHP-C arm will receive 1cc weekly injection of the study drug while the obese women receiving 500 mg of 17OHP-C will receive 2cc weekly injection during the study period. The clinical investigators will not be blinded to the study arm of participant [a) to track which patients receive which dose and b) so that the dose can be given to the treating physician should an adverse event occur], but the lab performing the pharmacokinetics studies will be blinded.

Administration of study drug: Administration of study drug will be performed by clinic staff in the office to ensure medication compliance. Although the patients will be enrolled into the study from as early as 12 weeks in preparation for the intervention, study medications will not be started until at least 16 weeks. The medication will be administered from between 16+0 weeks and 24 +6 weeks until 36 + 6 weeks gestation or until in preterm labor with advanced dilatation/delivery.

If the participant has already received the first prescription but has not yet taken any doses they would still be eligible to participate. They would not be able to return the medication to the pharmacy or

donate the medication. They could use their medication and then the remainder of the medication would be provided by the study.

Timeline of study visits: At the enrollment visit, a maternal blood draw to determine baseline 17P levels will be completed. Participants will then have the weekly visits with their obstetric care provider for the administration of the 17OHP-C injections, with the dose determined by the study arm to which they were allocated. They will also continue to have their scheduled prenatal care with their obstetric provider.

In addition to the routine prenatal care there will be Pharmacokinetic studies as described below.

Pharmacokinetic studies: Sampling schedule in order to investigate the pharmacokinetics of 250 mg 17OHP-C weekly as compared to 500 mg 17OHP-C weekly in obese women as well as 250 mg in non-obese women will be performed as follows:

- Using principles described by Caritis et al., four completed weeks of 17OHP-C therapy is required prior to sampling anticipating that steady state will be achieved by this time point.
- Follow-up sampling will be performed at these three time points:
- Sample #1: 20 22 weeks gestation
- Sample #2: 27 29 weeks gestation
- Sample #3: 34 36 weeks gestation

The blood draws will occur immediately before the weekly injection in order to obtain trough 17-OHPC levels.

Blood will be stored for future analysis into the use of 17OHP-C and preterm birth. The blood stored for future research will not contain any identifying information and will only contain the individual patient randomization number and the time (gestational age) when it was drawn.

Data Collection: Socio-demographic data of all enrolled subjects will be collected. These will include: maternal age, height, weight and body mass index (BMI), smoking, alcohol, socioeconomic status, ethnicity, parity and coexisting maternal medical disorders, previous and current pregnancy information, concomitant medications, and ultrasound examinations. While having the injections the site of the injection administration will be collected, and date and time of administration. Following delivery information from the delivery will be collected (pregnancy complications, type of labor, mode of delivery, delivery complications, gestational weight at delivery, birth weight, Apgar scores, cord blood gases, nursery admission and discharge information). Newborn outcome (respiratory distress, intraventricular hemorrhage, hypoglycemia, necrotizing enterocolitis, periventricular leukomalacia, seizures) and including any neurological assessment will also be collected.

d) Outcomes

- a. Primary Outcome: Mean trough levels of 17-OHPC in the three groups.
- b. Secondary outcomes of interest:
 - mean 17OHP-C plasma concentrations,
 - average peak concentration (Cmax)
 - half-life of 170HP-C
 - absorption, metabolism, volume of distribution, apparent clearance of 170HP-C
 - Gestational age at delivery
 - Preterm birth <37, 34, 32, 28 weeks

e) Data analysis

a. Sample Size Calculation:

We estimate the sample size for the study based on the primary aim and a number of assumptions:

- Trough concentrations (before next dose) for analysis²⁸
- Mean trough in normal weight women=11.0ng/mL (sd 5.0)²⁸
- Mean trough in obese women receiving 250mg =6.4 ng/mL (sd 4.0); assumed to be the dose below which efficacy is suboptimal²⁸
- Mean trough in obese women receiving 500mg =11.0 (sd 5.0); double dose assumed to return concentration to that for 250mg dose in normal weight women
- Alpha=0.05/2=0.025 (Bonferroni correction for 2 comparisons [normal 250mg vs obese 250mg and obese 500mg vs obese 250mg])
- Beta=0.02, Power=0.80
- Drop out rate=10%.

Sample size:

Based on the above assumptions we will enroll a total of 63 women with a prior history of spontaneous PTB (21 non-obese women, and 42 Obese women randomly assigned to 250 mg (n=21) or 500 mg (n=21) of weekly 17 OHP-C.

The breakdown of enrollment between University of South Florida affiliated sites and the Washington University in St. Louis affiliated sited is:

USF - 28 participants (6 non-obese women, and 22 Obese women randomly assigned to 250 mg (n=11) or 500 mg (n=11)

Washington University in St. Louis – 35 participants (15 non-obese women, and 20 Obese women randomly assigned to 250 mg (n=10) or 500 mg (n=10)

b. Data Analyses

The Student's t-test or Wilcoxon rank sum test will be used to compare levels of 17OHP-C and other continuous outcomes in obese women on 250 mg to obese women on 500 mg and to non-obese women on 250 mg. Categorical outcomes will be compared using the chi-squared or Fisher's exact test as appropriate.

Because this is a pilot study, the primary criterion for significance (p<0.05) will not be adjusted for multiple comparisons, in order the avoid missing a potentially significant effect. However, the secondary criterion will be P<0.025 (adjusted for the 2 comparisons).

f) Feasibility

- Potential Pitfalls: There is the potential to lose women to follow up due to the prospective design of the study. Several methods to improve study enrollment will be employed. First, 17OHP-C free of charge to the patients will be an incentive for enrollment. Second, the use of dedicated study staff will provide long-term continuity, and with whom the patient will develop rapport.
- b. *Training*: Before enrolling patients, all study staff will be trained on the study protocol, inclusion criteria, exclusion criteria, specimen collection, data collection and entry.
- c. *Leadership*: Successfully completing a prospective randomized trial is a challenging task. The experienced leadership of [name], [name] and [name] will ensure that obstacles encountered during the course of the trial are addressed in a constructive manner to continue moving forward with the project in a timely manner.

g) Timeline

Our goal is to complete the study within 1.5 years (18 months) including time to obtain the needed IRB approval, finalize protocol, recruit and start data analysis.

Study Timeline

Project Period (months)	0 - 3	4 - 16	16 - 18
Protocol development & IRB			
Subject recruitment			
Data collection & management			
Data analysis			
Drafting of manuscript & reports			

h) Ethical Aspects of the Proposed Research

- a. Human subjects' protection: All investigators will have completed Human Subjects' Protection training and their certification will be current. Investigators will explain the research and participation in the study in clear and simple language to ensure it is thoroughly understood by potential participants. Patients will be informed that they do not have to participate in the research, and their choice will not affect or alter their clinical care. This will be reinforced when informed consent is signed. Patients will be informed that they can withdraw their consent to participate at any time. A patient's capacity to understand and provide informed consent will be assessed when consent is obtained. If an investigator assesses that a patient does not understand the research or her decision, or the patient appears to be coerced, the investigator will make further assessments and discuss the situation with the PI to develop a management plan.
- b. Potential risks:
 - a. While every effort will be made to ensure protection of confidentiality, breach of confidentiality is a potential risk. To minimize this risk, a master list will be maintained linking the study ID to the patient data. This list will be doubly password protected (the computer and the file). The data will be also be in a double password protected file (the

computer and the file). Only members of the research team will have access to the research information.

- b. Blood draw: there may be some discomfort, bruising and /or minor bleeding at the site of the needle insertion. There is a very small risk of infection at the blood draw site and occasionally there may be light headedness, nausea and feeling faint.
- c. Intramuscular injection: there may be some redness, swelling, slight bleeding and minimal pain at the injection site. Rarely there may be swelling or inflammation.
- d. 17 OHP-C: injection site irritation (pain, rash, irritation, nodules, generalized swelling, hypersensitivity, warmth), allergic reactions (hives, urticarial, pruritus, facial swelling), digestive problems (nausea, diarrhea, vomiting), urinary tract infection, fever, fatigue, hot flashes, headaches and dizziness, respiratory problems (dyspnea, chest infection), depression and anxiety, decreased glucose tolerance, fluid retention, jaundice, and deep vein thrombosis/ pulmonary embolism.
- c. Potential benefits
 - a. The potential benefits of enrolling in the study include free administration of a drug that has been shown to decrease the risk of PTB by 33%.
 - b. Additionally, for the patients in the 500 mg 17 alpha hydroxyprogesterone caproate group, there is the potential benefit that it may decrease the rate of PTB more than the current regimen.
- d. Costs and Compensation: Women will receive free 17OHP-C as part of the protocol to enroll in this study.
- e.
- i) Safety Monitoring Plan

A safety monitoring plan will be established to review data from both recruitment sites. Washington University in St Louis will form their own monitoring plan to review the study on an ongoing basis.

At USF, the study PI and the study coordinator will review the data on an on-going basis, including paying special attention to women enrolled in the study with a diagnosis of depression to ensure that this does not worsen.

The PI at USF and Washington University in St Louis will follow up on a regular basis reviewing the enrollment and any safety issues.

On a 6 monthly basis, there will be a conference call between members of the study team at USF and members of the study team at Washington University in St Louis.

We will pay specific attention to edema, jaundice, blood sugar, and blood pressure.

References:

1. Practice bulletin no. 130: prediction and prevention of preterm birth. Obstetrics and gynecology. Oct 2012;120(4):964-973.

2. Hamilton BEPD, Martin JA, Osterman MMHS, Curtain SMA. Births: Preliminary Data for 2014. National vital statistics reports : from the Centers for Disease Control and Prevention, National Center for Health Statistics, National Vital Statistics System. Jun 2015;64(6):1-19.

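### The secondary aim concerns drug level and gestational age at delivery, but every planned analysis compares study groups and none uses a woman's measured trough as the exposure

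*Combined protocol and SAP*

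**What the plan says.** Three consecutive statements in the opening aims section do not share one exposure.

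- The aim: "Secondary Aim: Determine the relationship between maternal 17-OHPC levels and gestational age at delivery". The exposure is drug level.
- The hypothesis: "Higher doses of 17OHP-C will be associated with high gestational age of delivery in obese women". The exposure is dose, in obese women only.
- The analysis: "We will compare the mean gestational age at delivery of obese women receiving 250 mg to obese women receiving 500 mg", with the non-obese 250 mg group as a further comparator. The exposure is study group.

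Section C.d (Outcomes) lists plasma concentrations, gestational age at delivery and "Preterm birth <37, 34, 32, 28 weeks" as separate outcomes and does not link them. Section C.e.b (Data Analyses) says: "The Student's t-test or Wilcoxon rank sum test will be used to compare levels of 17OHP-C and other continuous outcomes", again between study groups, with chi-squared or Fisher's exact tests for categorical outcomes. There is no correlation, regression or level-category analysis. Section C.c schedules troughs at 20–22, 27–29 and 34–36 weeks, but names none of them as the exposure for the secondary aim.

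**The concern.** The rationale for the trial runs through drug level. The opening section links low plasma levels to spontaneous preterm birth, and section C.e.a assumes a level below which efficacy is suboptimal. The secondary aim is where the trial would look at that link in its own data, yet the plan would report gestational age by group only.

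Two things are at stake. First, the stated aim goes unanswered although troughs and delivery data are both collected. Second, if a level analysis is added later, the choice of trough, scale and covariates, and the handling of women who deliver early, would be made with the data in hand.

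**Working it through.** **1. What each planned contrast estimates.**

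| Contrast | What differs | What it estimates |
|---|---|---|
| Obese 500 mg vs obese 250 mg | Dose, randomised | Effect of dose assignment |
| Non-obese 250 mg vs obese 250 mg | BMI class, not randomised; same dose | Level and obesity together |
| Gestational age by measured trough | Level, woman by woman | The stated aim; not planned |

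Section B reports BMI as inversely related to trough, so the second contrast cannot separate level from obesity.

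**2. The plan's own figure.** Inputs from section C.e.a: means 11.0 and 6.4 ng/mL, SDs 5.0 and 4.0, alpha 0.025 (two-sided assumed), power 0.80. The printed beta of 0.02 does not match that power; 0.80 is used here.

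- Difference 11.0 − 6.4 = 4.6; mean variance (25 + 16)/2 = 20.5.
- n per group = 2 × 20.5 × (2.241 + 0.842)² / 4.6² = 18.4, so 19.
- Adding 10%: 19 × 1.1 = 20.9, so 21; 3 × 21 = 63.

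The 63 reproduces. It rests on trough differences between groups; no figure is given for the secondary aim.

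**3. How well group stands in for level.** Same inputs, equal group sizes; share = between-group variance / (between + within).

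- Obese arms (6.4 and 11.0): each mean lies 2.3 from the midpoint 8.7, so between = 2.3² = 5.29; within = 20.5; share = 5.29/25.79 = 0.205.
- Three groups (11.0, 6.4, 11.0): overall mean 9.47; between = (1.53² + 3.07² + 1.53²)/3 ≈ 4.70; within = (25 + 16 + 25)/3 = 22.0; share = 4.70/26.70 = 0.176.

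About 79% and 82% of trough variance therefore lies within groups, where the planned tests do not look. Part of that is assay and within-woman noise, so these shares are upper bounds on the extra information a regression could use.

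**4. What an added regression could detect.** After 10% dropout, 21 × 0.9 = 18.9, taken as 19 per group: 57 women. Fisher z, two-sided 0.05, power 0.80, k covariates: r = tanh(2.802/√(n − 3 − k)).

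- n = 57, k = 0: 2.802/√54 = 0.381, r = 0.36.
- n = 57, k = 2: 2.802/√52 = 0.389, partial r = 0.37.
- n = 51, k = 2 (six more women without a usable sample, an assumption): 2.802/√46 = 0.413, partial r = 0.39.

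The adjusted values are partial correlations and are not directly comparable with 0.36.

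**5. Selection on being undelivered at the draw.** The documents give no gestational-age distribution, so one is assumed: 42 minus a gamma variable (shape 1.8, scale 2.6), mean 37.3 weeks, SD 3.5, with a correlation of 0.4 with level set on the normal scale. About 1.5% then deliver before 27 weeks and 4.2% before 30 weeks. Dropping those women shrinks the slope by about 14% and 26% respectively. Building in the dependence another way changes these values, so they are illustrative.

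**6. Timing against the four-week rule.** Section C.c requires four completed weeks of therapy before sampling and permits starts from 16+0 to 24+6, which is 63 possible days. Counting back 28 days from 27+0 gives 23+0. Starts from 23+1 to 24+6 (13 of the 63 days) do not meet the rule when the 27–29 week window opens; a start at 24+6 meets it only from 28+6.

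**The case against.** The strongest reply is that the protocol does say how it will address the aim. A group comparison stands directly beneath it, the hypothesis and the randomised comparison agree, and the only loose element is the word levels in one sentence. On that view a rewording is enough. The aim is also secondary, the sample size is built on the primary aim, and the plan gives its status openly: "Because this is a pilot study, the primary criterion for significance" is left unadjusted.

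Part of this stands. The randomised comparison is a proper test of the dose hypothesis, and rewording would remove the contradiction. Pilot status justifies an exploratory label for any level analysis. It does not turn a dose or BMI contrast into an estimate of the level–outcome relation, and rewording gives up a question the collected data could address.

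Three stronger readings are tempting, and the documents do not support them.

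- A reader might infer that the primary result or the sample size is compromised. Neither depends on the secondary aim.
- A reader might infer that the sponsor intends to take a null group comparison as showing that level does not matter. No section plans that inference; it is only a possible misreading.
- A reader might want a power figure for group as a stand-in for level. That needs a level–outcome correlation, the share of trough variance that is true level, a linear relation, and dose acting only through level. The documents supply none of these, so no such figure is given here.

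**Conclusion.** The mismatch is in the text and needs no assumption: the aim is about level, the hypothesis about dose, and every planned analysis about group. Only the size of the gap uses numbers. The shares of about 21% and 18% follow from the section C.e.a planning means and SDs on the raw scale with equal groups. The detectable correlations assume 57 down to 51 women and a two-sided 0.05 test. The 14–26% shrinkage rests wholly on an assumed distribution and correlation. This should be settled before analysis, as a limit on what the secondary aim can report.

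**What to change.** Keep the randomised obese 250 mg versus 500 mg comparison as the test of the dose hypothesis, and add to section C.e.b one prespecified exploratory regression:

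- **Model.** Gestational age at delivery on a single named trough, for example the log of the 27–29 week trough among women undelivered at that draw, adjusted for continuous BMI and site. Report the slope with its 95% CI. BMI adjustment is prudent given its reported relation to trough; section B describes its link to preterm birth as conflicting.
- **Exposure.** Do not average all available troughs: the number of samples depends on when the woman delivers, so the average would depend on the outcome.
- **Selection.** Count by group the women who delivered before the draw, and state that most or all births before 28 weeks drop out of this analysis.
- **Sampling rule.** Flag samples drawn before four completed weeks of therapy and repeat the regression without them.
- **Optional.** A delayed-entry time-to-delivery model as a sensitivity analysis, noting that it also conditions on being undelivered.

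Fallback, if no level analysis is wanted: reword the aim to the effect of dose on gestational age at delivery in obese women, treat the non-obese group as descriptive, and draw no conclusion about level.

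Cost: one regression, one repeat and an optional sensitivity model on data already collected, with no extra visits or samples. The result is observational, can detect only moderate correlations, and is likely to be attenuated by selection on being undelivered. The fallback costs a sentence.

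### Gestational age at delivery is compared without adjusting for the gestational age of the qualifying preterm birth, which gives up some precision and protection against chance imbalance

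*Combined protocol and SAP*

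**What the plan says.** All references are to the combined protocol and SAP.

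- **Secondary Aim:** "We will compare the mean gestational age at delivery of obese women receiving 250 mg to obese women receiving 500 mg". The same sentence adds a comparison with non-obese women on 250 mg. Gestational age at delivery is also listed as a secondary outcome under Outcomes.
- **Data Analyses:** "The Student's t-test or Wilcoxon rank sum test will be used to compare levels of 17OHP-C and other continuous outcomes". No covariate, regression or stratified analysis is named anywhere.
- **Initial Enrollment:** before a woman is invited to take part, her records must confirm that the earlier preterm birth was of a "live born singleton gestation between the gestational ages of 20 weeks and 36 weeks and 6 days".
- **Data Collection:** the items include "previous and current pregnancy information", but the gestational age of the qualifying birth is not itemised.
- **Randomization:** "The randomization will be computer generated", with consecutive envelopes. No stratification on prior gestational age is stated.
- **Sample size:** "42 Obese women randomly assigned to 250 mg (n=21) or 500 mg (n=21". The calculation rests on trough level, not on gestational age.

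**The concern.** Eligibility cannot be checked without knowing how early the qualifying birth was. Every woman therefore has a pre-randomisation history of the quantity that later serves as the outcome, and its permitted range spans almost 17 weeks. If this history predicts the current pregnancy, leaving it out leaves explainable variation in the error term. With about 20 women per arm and no balancing on it, one arm may by chance hold women whose earlier births came sooner, and part of that difference would appear as an apparent dose effect in either direction.

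Timing matters too. Clinical investigators know the assigned dose, so an adjustment chosen after an imbalance has been seen would be open to challenge. One chosen now would not.

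**Working it through.** **Plan's own figure.** From the sample size section: trough means 11.0 and 6.4 ng/mL (difference 4.6), SDs 5.0 and 4.0, alpha 0.025 (taken as two-sided), power 0.80.

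n per arm = (5.0² + 4.0²) × (2.241 + 0.842)² / 4.6² = 41 × 9.505 / 21.16 = 18.42, so 19. Allowing for 10% dropout, 18.42 / 0.9 = 20.5, so 21 per group and 63 in total. The stated size reproduces, and about 19 per arm (21 × 0.9 = 18.9) would be evaluable.

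**Assumptions.** The documents give no SD for gestational age at delivery and no correlation r with prior gestational age. I take r from 0 to 0.5 and, where weeks are needed, an SD of 4 weeks. The formulas assume a common slope and a roughly normal covariate.

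**Precision.** With N women in the two obese arms, the variance of the adjusted difference relative to the unadjusted one is (1 - r²) × (1 + 1/(N - 4)). The second factor is the cost of estimating the slope. For N = 38 it is 1 + 1/34 = 1.029.

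| r | Variance ratio | Change |
|---|---|---|
| 0 | 1.029 | +3% |
| 0.2 | 0.96 × 1.029 = 0.988 | -1% |
| 0.3 | 0.91 × 1.029 = 0.937 | -6% |
| 0.4 | 0.84 × 1.029 = 0.865 | -13% |
| 0.5 | 0.75 × 1.029 = 0.772 | -23% |

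Break-even: r = √(1 - 1/1.0294) = 0.17.

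In weeks, the unadjusted SE is 4 × √(2/19) = 1.298, and the 95% half-width is 2.028 × 1.298 = 2.63. Adjusted, it is 2.030 × 1.298 × √0.937 = 2.55 at r = 0.3, and 2.030 × 1.298 × √0.772 = 2.31 at r = 0.5.

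In power terms at two-sided 0.05, the unadjusted test reaches 80% for a difference of 0.93 SD. At that difference the adjusted test has 79.2%, 80.4%, 82.4%, 85.3% and 89.0% at r = 0.1, 0.2, 0.3, 0.4 and 0.5.

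**Chance imbalance.** In its own SD units, the between-arm difference in mean prior gestational age has standard error √(2/n), which is 0.324 for n = 19 and 0.309 for n = 21. With 19 per arm it exceeds 0.5 SD in either direction with probability 2 × [1 - Φ(0.5/0.324)] = 12%, and 0.3 SD with probability 36%.

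An imbalance reaches the outcome only through the slope. For a 1-SD imbalance the shift is r × SD of outcome × √(2/n). With SD 4 and 21 per arm:

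- r = 0.3: 0.3 × 4 × 0.309 = 0.37 weeks
- r = 0.5: 0.5 × 4 × 0.309 = 0.62 weeks

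A simulation of 20,000 trials reproduced the variance ratios to within about 0.01. In runs where one arm was ahead by more than 0.5 SD (19 per arm), the unadjusted difference was off on average by about 0.21 SD at r = 0.3 and 0.32 SD at r = 0.5; the adjusted difference was off by about 0.

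**The case against.** The other side has a good case, and much of it stands.

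- **No error of validity.** A reader might infer that the unadjusted obese comparison is biased. The documents do not support that: dose is randomised, so the planned tests are valid. Variation from chance imbalance is already inside the unadjusted SE, so the precision and imbalance results are two views of one loss and must not be added.
- **Imbalance does not carry over in full.** A reader might suppose that a difference of a week or more in prior gestational age (3.5 × √(2/21) = 1.1 to 4.5 × √(2/21) = 1.4 weeks, for an assumed covariate SD of 3.5 to 4.5) appears whole in the result. Only slope times imbalance does, which gives the 0.37 to 0.62 weeks above.
- **The gain is not assured.** Only data collection is nearly free. Prior births are confined to 20 weeks to 36 weeks 6 days, and truncating a covariate usually weakens its correlation, so a low r is plausible. Below about 0.17 adjustment loses slightly. Even at r = 0.5 the interval remains wider than ±2 weeks.
- **Skewness does not condemn the planned tests.** In a simulation with skewed errors at 19 to 21 per arm, the t-test rejected in 4.6 to 5.0% of null trials. Uncorrected robust errors with a normal reference rejected in about 6.5%, and HC3 in about 3.9%. A robust-error option therefore needs a small-sample correction.
- **Adjustment does not repair the non-obese contrast.** That group is not randomised. Site mix also differs by plan: 15 of 21 non-obese women (71%) against 20 of 42 obese women (48%) come from Washington University. The Background links higher BMI to spontaneous preterm birth, so prior gestational age may itself reflect obesity, and adjusting could remove part of the difference of interest.

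The Secondary Aim is also worded as a relationship between drug level and gestational age, and this change does not address that. It is a separate matter.

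These points limit the size of the concern. They do not remove the case for naming the covariate in advance.

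**Conclusion.** The point holds as a minor one. The plan confirms a relevant baseline value for every woman before randomisation and then does not use it, so the obese 500 mg against 250 mg comparison gives up some efficiency and some protection against chance imbalance.

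The range runs from a trivial loss if the correlation is near zero to a worthwhile gain from about r = 0.3 upward. It rests on an assumed correlation, an assumed SD where weeks are quoted, and 19 evaluable women per arm inferred from the stated dropout. The documents fix neither the correlation nor the SD, so no single figure can be claimed. Severity stays low because gestational age is a secondary outcome, the trial was not sized on it, and the plan calls itself a pilot.

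**What to change.** 1. Prespecify a linear model of gestational age at delivery on randomised dose plus gestational age of the qualifying preterm birth, meaning the birth confirmed at eligibility, so that the choice is fixed if a woman has had several. Use ordinary model-based standard errors, or a small-sample-corrected version such as HC3 with a t reference.
2. List that gestational age as an explicit item under Data Collection.
3. Report the adjusted 500 mg against 250 mg difference with its 95% CI, and keep the unadjusted comparison as supportive.
4. Label the non-obese contrast observational. State that adjusting for this one variable does not remove confounding and that prior gestational age may itself reflect obesity.

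**Cost:** a few sentences and one data field, drawn from records already reviewed. Statistically, it takes one degree of freedom and up to about 3% in variance if the correlation is near zero.
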